## Revision Chronology

GlaxoSmithKline Document Number	Date	Version
2013N167482_00	2014-APR-16	Original
2013N167482_01	2014-SEP-05	Amendment No. 1
Reason for Amendment 01:		

Changes have been made to safety related study specific dose adjustment criteria following MHRA review.
 
An update has been made to the exclusion criteria of the protocol Section 4.2.2. and a change has been made to Section 10.2 Regulatory and Ethical considerations following German (Berlin) Ethics Committee review.
		
2013N167482_02	2014-DEC-10	Amendment No. 2
Reason for amendment 02:		

Changes have been made to list all of the challenge agents to be used in the study following guidance from German Regulatory Agency (BfArM).
 
A table of the list of challenge agents has been added to the study treatment section. An update to the skin prick test procedure and the correct name of one of the challenge agents has been added to the inclusion criteria.
		
2013N167482_03	2015-JUN-07	Amendment No. 3

Part B and C have changed from a bilateral to a placebo-controlled randomised parallel design 3:1 active to placebo.
 
An informal review of data from the first 4 patients of Part B will be performed before starting part C
 
The number of subjects in Part C has increased (from n=12 up to n=16); and a 2-week PK, safety and biomarker endpoints sampling period for parts B & C has been implemented
		
2013N167482_04	2016-APR-11	Amendment No. 4

Updates have been made following the interim analysis of the first 4 subjects in Part B, related to the dosing in Parts B and C.
 
A change has been made to the inclusion and exclusion criteria, related to use of contraception for women of child bearing potential.
		

Changes have been made to the PK sampling time points for Part C.		
2013N167482_05	2016-OCT-13	Amendment No. 5
Administrative amendment to account for the change in primary medical monitor, as documented in the Medical Monitor and Sponsor Contact Information table.		
In addition, the following corrections have been made that were previously captured in a note to file format. The following file note is hereby superseded:		

• File note dated 26th April, 2016 concerning two clarifications of typographic/edits errors: Timing of tolerability assessment, and timing of the complete physical exam. These have been updated in Section 6.1.4

		

2013N167482\_05

CONFIDENTIAL

200196

## LIST OF ABBREVIATIONS

AAS	Angioedema Activity Score
AE	Adverse Event
AUC	Area Under the Curve
BCR	B Cell Receptor
BHR	Basophil Histamine Release
BMI	Body Mass Index
BPM	Beats Per Minute
BSA	Body Surface Area
CL bq	Blood Clearance
C max	Peak plasma concentration of a drug after administration.
CPMS	Clinical Pharmacokinetics Modelling and Simulation
CsU	Chronic Spontaneous Urticaria
CTT	Critical Temperature Threshold
CU	Cold urticaria
CuQ2oL	Chronic Urticaria Quality of Life Questionnaire
DLQI	Dematology Life Quality Index
DMPK	Drug Metabolism and Pharmacokinetics
ECG	Electrocardiogram
eCRF	Electronic Case Report Form
Fc $\epsilon$ R1	Fc Epsilon receptor
FSH	Follicle Stimulating Hormone
GCSP	Global Clinical Safety and Pharmacovigilance
HBsAg	Hepatitis B surface Antigen
hCG	Human Chorionic Gonadotrophin
HIV	Human Immunodeficiency Virus
HRT	Hormone Replacement Therapy
IB	Investigator's Brochure
IgE	Immunoglobulin E
IUD	Intrauterine Device
IUS	Intrauterine System
IV	Intra venous
MABEL	Minimum Anticipated Biological Effect Level
MSDS	Material Safety Data Sheet
NOAEL	No Observed Adverse Effect Level
NOEL	No Observed Effect Level
PD	Pharmacodynamic
PK	Pharmacokinetic
PUVA	Psoralen combined with Ultraviolet A
QOL	Quality of Life
QTcF	QTc interval Friderica's
RAP	Reporting Analysis Plan
SAE	Serious Adverse Event
SAE	Serious Adverse event
SMC	Safety Monitoring Commitee
SPM	Study Procedures Manual
SPT	Skin Prick Test

SYK	Spleen Tyrosine Kinase
Tmax	The time of Cmax occurring
TSH	Thyroid Stimulating Hormone
UAS7	Urticaria Activity Score
VAS	Visual Analog Scale
Vss	Volume of distribution at Steady State

## Trademark Information

Trademarks of the GlaxoSmithKline group of companies	Trademarks not owned by the GlaxoSmithKline group of companies
NONE	Chiron RIBA Dapsone Inform Phoenix (includes WinNonlin) Zaditen

## 1. INTRODUCTION

### 1.1. Study Rationale

This First Time in Human (FTIH) study, which will be performed in three parts is designed to investigate the safety, tolerability, pharmacokinetics and pharmacodynamics after single and repeat topical applications of up to 2 strengths of GSK2646264 and corresponding placebo, in:

- healthy adult subjects (Part A)
- subjects with cold urticaria (CU, Part B)
- subjects with chronic spontaneous urticaria (CsU, Part C)

The study will also measure short term effects of GSK2646264 on the number and size of weals in subjects with CsU, the area and volume of weals following an allergen skin prick test in healthy volunteers and patients and a disease specific challenge (cold temperature test) for comparison of mechanism with the allergen skin prick test in the cold urticaria subjects.

### 1.2. Brief Background

Spleen tyrosine kinase (SYK) is an intracellular protein tyrosine kinase involved in the downstream signalling events of several immunoreceptors in a variety of cell types, notably the B-cell receptor (BCR), the IgG receptors (Fc $\gamma$ RI and III) and the Fc epsilon receptor (Fc $\epsilon$ R1). These immunoreceptors including the Fc $\epsilon$ R1, the high affinity receptor for IgE, are important in contributing to the pathology of IgE mediated diseases such as chronic urticaria, and thus pharmacological inhibition of these kinases could be beneficial in these predominantly mast cell driven diseases.

Chronic urticaria is a common skin disease with up to 1% of the population affected ([Maurer](#), 2011a). It is characterised by daily or almost daily itchy weals on the skin, with or without angioedema, that last for greater than 6 weeks. The classification of chronic urticaria includes six distinct patterns of which two will be investigated in this study.

Cold urticaria, a form of inducible urticaria, characterised by local skin reactions consisting of itchy weal and flare responses following cold exposures. These reactions can be induced on discrete areas of the skin using an electronic device called a TempTest thus allowing a critical temperature threshold (CTT) to be established. CTT and changes in CTT values can be correlated with disease severity and changes in disease activity respectively ([Mlynek](#), 2010).

Chronic spontaneous urticaria characterised by itchy weals for greater than 6 weeks is thought in part to be mediated by auto-antibodies against the Fc $\epsilon$ R1 or IgE which bind to the Fc $\epsilon$ R1 on mast cells and basophils leading to the degranulation and release of pro-inflammatory mediators from these cells ([Greaves](#), 2000).

Chronic urticaria can be difficult to treat, with patients demonstrating a variable response to first-line therapies including oral H1 antihistamines. Second and third line treatments

include leukotrienes, cyclosporine and short term treatment with oral corticosteroids if no efficacy is obtained after increased dosage of antihistamines.

SYK inhibition, following IgE activation of the Fc $\epsilon$ R1, will reduce three main mast cell functions: the release of preformed mediators such as histamine, the secretion of cytokines including TNF alpha and the production of leukotrienes and prostaglandins. The majority of drugs currently used to treat IgE-mediated disorders target a single mediator e.g. antihistamines or leukotriene modifiers. The SYK inhibitor GSK2646264 should stabilise the mast cells and prevent multiple mediators from being released. The dose-dependent inhibition of histamine release with GSK2646264, after anti-IgE stimulation in ex-vivo human skin, supports the potential for the use of this compound as a treatment for chronic urticarias.

To further support this rationale, recent Phase 3 clinical trials of Omalizumab, a humanised monoclonal anti-IgE antibody which binds to free IgE preventing the interaction between IgE and mast cells or basophils, was shown to reduce clinical signs and symptoms in patients with chronic spontaneous urticaria who had not responded to H1 antihistamine therapy (Saini, 2011), (Maurer, 2011a). This data has supported an EMEA approval in adult and adolescent (12 years and above) patients with inadequate response to H1 antihistamine treatment.

Additionally, Omalizumab has shown benefit in a small population of cold urticaria patients and Phase 2 trials for this condition (Clinical Trials for Cold urticaria <http://clinicaltrials.gov/ct2/show/ NCT01580592>) are underway.

As SYK is downstream of the Fc $\epsilon$ R1, a similar inhibition of this pathway is likely to occur in the presence of a SYK inhibitor suggesting that GSK2646264 may be beneficial in chronic spontaneous urticaria, cold urticaria and other skin disease where omalizumab shows improvement in disease activity.

## 2. OBJECTIVE(S) AND ENDPOINT(S)

### 2.1. Primary objectives and endpoints for all study parts (A, B & C)

Objectives	Endpoints

Safety and Tolerability
 
To investigate the safety and tolerability of topically applied GSK2646264 cream and its placebo in healthy subjects, subjects with cold urticaria (CU1) and subjects with chronic spontaneous urticaria (CsU).
	
Safety and Tolerability
 
 
Number, severity and frequency of AEs and serious AEs (local and systemic)
 
heart rate
 
blood pressure
 
12- lead ECG
 
clinical laboratory safety tests
 
assessment of the local tolerability of the study medication
 

1. All Healthy subjects and the Cold urticaria subjects should be screened for reactivity to one of the allergens used in skin prick test. (grass pollen, Dermatophagoides pteronyssinus, birch pollen and cat dander)

## 2.2. Secondary objectives and endpoints for all study parts (A, B & C)

Objectives	Endpoints
Pharmacokinetics in plasma  To evaluate the plasma concentrations of GSK2646264 in Healthy, CU and CsU subjects	Pharmacokinetics in plasma 
 
Plasma concentrations of GSK2646264 and pharmacokinetic parameters, including AUC, Cmax, Tmax, t1/2 if data allows
 

## 2.3. Exploratory Objectives and Endpoints

### 2.3.1. Part A: Healthy Subjects

Objectives	Endpoints
Exploratory  Pharmacodynamic measure of Allergen Challenge  Assess measure of weal and flare size and erythema, in healthy subjects after allergen challenge (Skin Prick test, positive control (histamine) and negative control (saline)).  
 
Duration of response in healthy subjects
 
	Pharmacodynamic measure of Allergen Challenge 
 
Percent inhibition on days 1,3, 4 and 6 will be derived for:               
 
The longest weal diameter (measured by ruler).
 
Perpendicular weal length (measured by ruler).
 
Weal area calculated using weal diameter and length assuming ellipse area.
 
 
 
Weal Volume as measured by:               
 
Quantitative volumetric morphometry
 
 
 
Flare erythema as measured by               
 
Mexameter
 
 
 
 
Percent of inhibition at 24 hours post final dose, will be derived for the endpoints above

1. Measured using digital camera using PRIMOS 5.075D instrument software produced by GMF

2. Measures erythema and melanin index values using narrow band spectrophotometry

### 2.3.2. Part B: Cold urticaria Subjects

Objectives	Endpoints
Exploratory	
Pharmacodynamic measure of Cold Provocation Assess change in Cold Temperature Test values	Pharmacodynamic measure of Cold Provocation 
 
Change from placebo of Cold Temperature Test values at day 3
 

Pharmacodynamic measure of Allergen Challenge Assess measure of weal and flare size, in subjects with Cold urticaria after allergen challenge (Skin Prick test, positive control (histamine) and negative control (saline)).	Pharmacodynamic measure of Allergen Challenge 
 
Percent of inhibition on day 3 will be derived for:               
 
The longest weal diameter (measured by ruler).
 
Perpendicular weal length (measured by ruler).
 
Weal area calculated using weal diameter and length assuming ellipse area.
 
 
 
Weal Volume as measured by;               
 
Quantitative volumetric morphometry
 
 
 
Flare Erythema as measured by;               
 
Mexameter
 
 
 

Systemic measure of target pharmacology Determine CD69 expression in an ex vivo blood sample following CD69 stimulation	Systemic measure of target pharmacology 
 
Percent inhibition of CD69 expressing cells in blood samples stimulated with anti-IgM .
 

1. Measured using digital camera using PRIMOS 5.075D instrument software produced by GMF
2. Measures erythema and melanin index values using narrow band spectrophotometry
3. TEMPTest 4.0

[figure not shown]
### 2.3.3. Part C: Chronic Spontaneous Urticaria Subjects

Objectives	Endpoints
Exploratory	
Pharmacodynamics as assessed by the Urticaria activity score  Urticaria Activity Score: Assess measures of weal characterisation in CsU subjects within treated area only	Pharmacodynamics as assessed by the Urticaria activity score 
 
Urticaria Activity Score, a composite score using key urticaria symptoms (number of weal, itch/pruritus), to derive change from baseline for the 7 days after dosing
 

To measure of Quality of Life	
 
Dermatology Life Quality Index (DLQI) questionnaire
 

To measure disease activity	
 
Angioedema Activity Score (AAS)
 

Investigate relationships between (basophil histamine release) BHR test and weal characteristics	
 
Relationship of positive BHR test with reduction in number or size of weals
 

Systemic measure of target pharmacology  Determine CD69 expression in an ex vivo blood sample following CD69 stimulation	Systemic measure of target pharmacology 
 
Percent inhibition of CD69 expressing cells in blood samples stimulated with anti-IgM.
 

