GSK2646264 cream or placebo cream will be applied to a given BSA once per day, every 3 days, on days 1, 4 and 7, on areas of the body chosen by the investigator. The areas where cream is applied will remain the same for each day of dosing. The 10 % BSA can be distributed between the arms, legs and torso for an individual subject and will be decided by the investigator prior to randomisation. This pattern of cream application will remain the same for the duration of dosing. The maximum % BSA and the frequency of dosing will be decided after Part A and n=4 in Part B of the study but will not exceed 20% BSA.

The subjects will be dosed in the unit for the first dose on day 1 and then discharged from the clinic. Subjects will return to the clinic prior to the dose and specified assessments on days 4 and 7. Subjects will be asked to complete a daily diary over the 7 days. Details of the diary will be provided in the Study Procedures Manual (SPM)

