#### **4.2.1.4. Additional Inclusion criteria specific for subjects with chronic spontaneous urticaria (Part C)**

Subjects will be included in the chronic spontaneous urticaria cohort if all the following criteria apply

1. The subject is aged between 18 and 70 years of age inclusive, at the time of signing the informed consent.
2. Body weight  $\geq$  50 kg and BMI within the range 19 to 35 kg/m^2 (inclusive)
3. Subjects who have a score of  $>14$  on the UAS7 questionnaire with between 4-20 weals observed in a defined area of the body will be included in this study. This area must include either arms, legs or torso for 7 consecutive days during the screening period, prior to the Day 1 visit. If a subject has not completed 7 consecutive days of UAS questionnaire prior to dosing on Day 1 due to exceptional circumstances, the screening period may be extended until the subject has completed 7 consecutive days of UAS questionnaire. This will only be at the discretion of the Investigator.
4. No other aetiology identified for chronic urticaria such as drug-related or inducible urticaria as determined by history, physical examination and laboratory studies.
5. Subjects must be free from any past or present benign or malignant skin conditions and disease, other than the specified condition required for eligibility of subjects as defined in the specific inclusion criteria for CsU cohort unless in the opinion of the investigator it will not compromise the subjects safety and quality of data.

6. Other than a diagnosis of chronic spontaneous urticaria the subject should have no other co-morbidities which would introduce additional risk factors and will not interfere with the study procedures, as determined by a responsible and experienced physician, based on a medical evaluation including medical history, physical examination, laboratory tests and cardiac monitoring.
7. A subject with a clinical abnormality or laboratory parameter(s) which is/are not specifically listed in the inclusion or exclusion criteria, outside the reference range for the population being studied may be included only if the Investigator, in consultation with the GSK Medical monitor if required, agrees and documents that the finding is unlikely to introduce additional risk factors and will not interfere with the study procedures.

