### URTICARIA ACTIVITY SCORE - 7 (UAS-7) DIARY

1. Wheals  yes →  no ↓	
 
 
How many wheals/ erythemas have appeared during the last 24 hours?
 
 <20    <1 cm    <1 cm    <3 hrs    <3 hrs
 
 20-50    1-5 cm    1-5 cm    3-12 hrs    3-24 hrs
 
 >50    >5 cm    >5 cm    >12 hrs    >24 hrs
 
 
 
What average size did these wheals/ erythemas have during the last 24 hours?
 
 <20    <1 cm    <1 cm    <3 hrs    <3 hrs
 
 20-50    1-5 cm    1-5 cm    3-12 hrs    3-24 hrs
 
 >50    >5 cm    >5 cm    >12 hrs    >24 hrs
 
 

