2. Erythema  yes →  no ↓	
 
 
What was the size of the largest wheal/ erythema during the last 24 hours?
 
 <20    <1 cm    <1 cm    <3 hrs    <3 hrs
 
 20-50    1-5 cm    1-5 cm    3-12 hrs    3-24 hrs
 
 >50    >5 cm    >5 cm    >12 hrs    >24 hrs
 
 
 
For how many hours did you have wheals/ erythemas during the last 24 hours?
 
 <3 hrs    3-12 hrs    >12 hrs    >24 hrs
 
 

3. Angioedema  yes →  no ↓	
 
 
Please choose the category that best describes your angioedema(s) during the last 24 hours?
 
 small / mild    mild
 
 moderate    moderate
 
 large / severe    severe
 
 
 
How severe were the complaints caused by edema during the last 24 hours?
 
 mild    moderate
 
 moderate    severe
 
 

4. Itch/ Pruritus  yes →  no ↓	
 
 
How many hours did you experience itch during the last 24 hours?
 
 <3 hrs    3-12 hrs    >12 hrs
 
 
 
How severe was the itch during the last 24 hours?
 
 mild    moderate
 
 moderate    severe
 
 

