
 To assess the pharmacodynamic effect of GSK2646264 on weal and flare sizes and erythema, in cold urticaria subjects after allergen challenge (Skin Prick test, positive control (histamine) and negative control (Saline)). 	
 Percent inhibition on days 1, and 3 for the longest weal diameter (measured by ruler). Percent inhibition on days 1, and 3 for perpendicular weal length (measured by ruler). Percent inhibition on days 1, and 3 for weal area (calculated). Percent inhibition on days 1, and 3 for Weal volume (measured by quantitative volumetric morphometry¹) Percent inhibition on days 1, and 3 for Flare erythema (measured by Mexameter²).

 To assess the effect of GSK2646264 on Cold Temperature Test values 	
 Change in Cold Temperature Test⁴ values at day 1 and day 3
Part C: Chronic Spontaneous Urticaria Subjects	Part C: Chronic Spontaneous Urticaria Subjects

 To assess the effect of GSK2646264 on weal characterisation in CsU subjects within treated area only To assess the Quality of Life in CsU subjects. To assess the disease activity in CsU subjects. To investigate the relationships between (basophil histamine release) BHR test and weal characteristics 	
 Urticaria Activity Score, a composite score using key urticaria symptoms (number of weals, Itch/Pruritus), to derive change from baseline on Day 1 through to Day 7 Change from baseline in total Dermatology Life Quality Index (DLQI) score Change from baseline in Angioedema Activity Score (AAS) Relationship of positive BHR test with reduction in number or size of weals
1 All Healthy subjects and the Cold Urticaria subjects should be screened for reactivity to one of the allergens used in skin prick test. (grass pollen, Dermatophagoïdes pteronyssinus, birch pollen and cat dander) 2 Measured using digital camera using PRIMOS 5.075D instrument software produced by GMF 3 Measures erythema and melanin index values using narrow band spectrophotometry 4 TEMPTest 4.0 5 Calculated as ellipse or oval area	

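### The Part C weal objective is confined to treated skin, but the UAS7 diary names no body area and its weal bands miss most partial reductions there

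*Protocol*

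**What the plan says.** The objective is local in both documents. Protocol 2.3.3 reads "Assess measures of weal characterisation in CsU subjects within treated area only"; SAP 2.2 reads "To assess the effect of GSK2646264 on weal characterisation in CsU subjects within treated area only".

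The endpoint set against it in Protocol 2.3.3 is "Urticaria Activity Score, a composite score using key urticaria symptoms (number of weal, itch/pruritus), to derive change from baseline for the 7 days after dosing". Protocol 6.5.2.1 takes the components from the daily diary in Appendix 3 and adds the component scores. Protocol 9.3.2.3.2 sums seven days.

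The diary's weal question is "How many wheals/ erythemas have appeared during the last 24 hours", with answers under 20, 20-50 and over 50 behind a yes/no gate. Its itch question is "How severe was the itch during the last 24 hours", graded mild, moderate or severe. Neither mentions a body area. Weal size and duration are also asked, but SAP 9.1.2.1 only lists the unscored items.

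The cream goes on 10% BSA chosen by the investigator: "The 10 % BSA can be distributed between the arms, legs and torso for an individual subject" (Protocol 3.1.5). Subjects qualify with UAS7 above 14 and "with between 4-20 weals observed in a defined area of the body will be included in this study" (Protocol 4.2.1.4). That area is not stated to be the one later treated. Protocol 3.1.5 leaves further diary details to the Study Procedures Manual, which is not among the documents reviewed.

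**The concern.** The question is about treated skin and the measurement is not. The Part C schedule (Protocol 6.1.4) contains no other weal count, and no other scored diary item fills the gap. Reported as planned, a score covering the subject's urticaria in general would be presented as an effect on weals in the treated area.

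The inference could fail in both directions. A difference in UAS7 between arms could not be located in treated skin, and a null result would leave open a substantial local effect. Part C is meant to inform further clinical studies (Protocol 3.2.1.3). The basophil histamine release endpoint in Protocol 2.3.3 also depends on a reduction in weal number or size.

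**Working it through.** There is no plan figure to reproduce: Protocol 9.2 bases the sample size on feasibility and gives no effect size, SD or power for UAS7. The check compares weal counts with the diary's answer bands.

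**Inputs.** Bands: none, under 20, 20-50, over 50 (Protocol Appendix 3). Entry count in a defined area: 4 to 20, which is 17 whole numbers (Protocol 4.2.1.4). I treat the entry count as comparable with the diary's 24-hour count and as applying to the treated area; both are assumptions.

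**Reading 1: subjects count only the treated area.**
- Counts 4 to 19 fall in the lowest band: 16 of 17, or 94%.
- From any of these, a fall that leaves at least one weal stays in that band. For example, 19 to 1 is an (19 − 1)/19 = 95% reduction with no change of answer.
- Cuts of 25%, 50%, 75% and 90% change the band only from a start of 20, which is 1 of 17 starting values.

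**Reading 2: subjects count the whole body, as the printed question reads.** Let T be weals in the treated area and O weals elsewhere. The diary records the band of T + O.
- T = 12, O = 12: 24 weals. Halving T gives 18, and the band drops.
- T = 12, O = 5: 17 weals. Clearing T gives 5, and the band does not change.
- T = 12, O = 30: 42 weals. Clearing T gives 30, and the band does not change.

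Counting every pair with T = 4 to 20 and several ranges of O, with halved counts rounded to whole numbers:

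| O outside the area | Pairs | Band falls if T is halved | Band falls if T is cleared |
|---|---|---|---|
| 1-15 | 255 | 96 (38%) | 135 (53%) |
| 1-30 | 510 | 101 (20%) | 203 (40%) |
| 1-46 | 782 | 198 (25%) | 339 (43%) |
| 1-60 | 1020 | 203 (20%) | 407 (40%) |

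These grids are unweighted, so the percentages are not probabilities for patients. They show that clearing the area is neither necessary nor sufficient for the weal item to move.

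**What else moves the composite.** The documents give no points per answer, so assume 0-3 per item per day. A subject in the lowest weal band every day has 1 × 7 = 7 weal points a week.
- Entry above 14 means at least 15 points, so at least 15 − 7 = 8 come from itch: 8/15 = 53% of the score.
- With maximum itch the share is 21/(7 + 21) = 75%.
- The total can therefore fall from 15 to 7, or from 28 to 7, with no change of weal band.
- Each weal-free day takes off one further point.

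The score can respond, but the itch part carries no information about where on the body the response occurred.

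**The case against.** The strongest counter-case has four parts.

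**The score is not blind to partial effects.** A reader might infer that UAS7 cannot show a treated-area effect short of full clearance. The documents do not support that. Itch is more than half the score at the entry threshold under 0-3 scoring, weal-free days lower the weekly sum, and whole-body counts can cross a band after a partial fall. In particular, the fall from 19 to 1 does change the band on a whole-body count when 1 to 18 or 32 to 49 weals lie outside the area. It is hidden only at O = 0, 19 to 31, or 50 and above. This part stands in full, and the point is limited accordingly.

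**The Study Procedures Manual may restrict the diary to the treated area.** It may; Protocol 3.1.5 defers diary details to it, and nobody can say from these documents what it contains. But a restriction would only move the trial from Reading 2 to Reading 1, where the bands hide nearly every partial fall.

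**The dilution has no simple bounds.** One might argue that clearing 10% BSA lowers the whole-body count by between 10% (weals spread evenly) and 100% (all weals in the area). The lower figure is not a bound: if the treated skin carries less than its share of weals, the fall is smaller still. No such range is claimed here.

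**The stakes are modest.** The objective is exploratory and the primary objective is safety. With 16 subjects randomised 3:1, so 12 active and 4 placebo, a null UAS7 result would be weak evidence with any diary. Part C also has CD69, AAS and DLQI endpoints. This stands as to severity. It does not remove the mismatch between what the objective asks and what the diary records.

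**Conclusion.** The point holds in a limited form. The weal item is not specific to the treated 10% BSA, and it is too coarse to register most partial reductions there. On an area-only count, 16 of 17 entry counts share one band and partial falls register from only one starting value. On a whole-body count, halving the area's weals changes the band in 20-38% of the pairs examined, and clearing the area does so in only 40-53%.

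It follows that a UAS7 difference cannot be attributed to treated skin and that a null result does not exclude a local effect. It does not follow that Part C can show no drug effect, or that its other pharmacodynamic measures fail.

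The conclusion rests on the diary as printed, on applying the 4-20 entry range to the treated area, and, for the itch arithmetic only, on 0-3 points per item. The change should be made, but neither the safety objective nor any power claim depends on it.

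**What to change.** Leave the UAS7 items and scoring unchanged.

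1. Have the investigator define the treatment area before the seven-day screening diary starts. Protocol 3.1.5 already requires the choice before randomisation, but randomisation is on Day 1, after the baseline diary days.
2. Add one diary line, at baseline and post-dose, for the actual number of weals inside that area in the last 24 hours.
3. In Protocol 9.3.2.3.2 and SAP 9.1.2.1, name the seven-day change in this count, analysed by ANCOVA with treatment and baseline count, as the treated-area measure. Keep UAS7 as the general activity score.

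The cost is a small patient and translation burden, earlier definition of the area, a way for subjects to recognise its limits (the protocol describes no marking procedure), and some difficulty in self-counting on the torso. Eligibility already calls for weals to be observed in a defined area over seven screening days, so the task is not wholly new.

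If this is not wanted, restate the objective in Protocol 2.3.3 and SAP 2.2, and any conclusion drawn from it, as UAS7 not specific to the treated area. That costs only wording. If the Study Procedures Manual already restricts the diary, cite the instruction in both documents; that settles the area but not the banding.
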